6 STUDY INTERVENTION

6.1 STUDY INTERVENTION(S) ADMINISTRATION

6.1.1 STUDY INTERVENTION DESCRIPTION

Chemistry, Manufacturing, and Control:

Study Agent: Resveratrol

[figure not shown]
Established Name: Trans-Resveratrol Trade Name: Vita-Age 98% Pure Trans Resveratrol Manufacturer by Vita-Age, [name] under Good Manufacturing Practices (GMP) Extracted from Japanese Knotweed Root Dosage Form: Relabeled bottled containing size 00 capsules of resveratrol from commercially available bottles. Labeling with reflect the route of administration for this study. Strength: 500mg resveratrol per capsule Route of Administration: 2 oral capsules 4 times per day Lot Number for resveratrol raw material: U-F-HZ20200110 (88260-1) Certificate of Analysis #1 by Vita-Age (see appendix 12.1.2a)

Lot Number for prepared capsules: 20680

Certificate of Analysis #2 for prepared capsules by Labs-Mart Inc, [name] (see appendix 12.1.2b)

PubChem CID for resveratrol: 445154 https://pubchem.ncbi.nlm.nih.gov/compound/Resveratrol Product Label in English (see appendix for full label):

[figure not shown]

Study Agent: Placebo

[figure not shown]
Established Name: Placebo Manufacturer by Vita-Age, [name] under Good Manufacturing Practices (GMP) Dosage Form: Size 00 capsules containing brown rice flour (sourced from Moore's Flour Mill, [name]) to be prepared to be visually indistinct from the treatment capsules. Rice starch is Generally Recognized as Safe (GRAS) NTIS# PB80128804 Route of Administration: 2 oral capsules 4 times per day Lot Number of brown rice flour: 041620 Certificate of Analysis for Stabilized Brown Rice Flour (see appendix 12.2.1). Lot Number of prepared capsules: 20677 Certificate of Analysis for prepared Placebo Capsules (see appendix 12.2.2)

Study Agent: Vitamin D3

Established Name: Cholecalciferol Manufacturer: Ortho Molecular Products, [name]. Dosage Form: 50,000 I.U. Route of Administration: Two capsules once (100,000 IU total), orally on day 1 of the study provided in factor sealed blister pack. Batch Number: WIP LOT# 83654 Certificate of Analysis: See Appendix 12.3.3 PubChem CID for Cholecalciferol: 5280795 https://pubchem.ncbi.nlm.nih.gov/compound/5280795

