During the enrollment process and after providing consent to participate, subjects will complete a short, online form providing their contact information. Subjects will also be asked to provide the contact information of a spouse, family member or other person in the event the investigator or study personnel lose contact with the subject, so that the subject's status can be determined. The online form is HIPAA-compliant and meets HIPAA regulations for data security. Completion of the form will generate an anonymous study ID associated with that subject and which will be used for other study-related data collection. The study ID does not use any HIPAA-designated identifiers such as birthdate, social security number, etc.

Randomization: The random allocation list will be blocked and stratified by a third-party group or individual. During the trial, only the third-party group and DSMB will have access to the randomization

list, which will be stored on a password-protected computer and/or password-protected file (e.g., REDCap, Excel) by the third-party group or individual. The study personnel will create identical-looking packets with identical-appearing study agents containing a 15-day dosing regimen according to the random allocation list. Study personnel will be blinded to the contents of the distributed packets.

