6.1.2 DOSING AND ADMINISTRATION

Treatment Group: Two capsules containing resveratrol 500mg each will be taken 4 times per day. A 15day supply of 120 capsules in manufacturer sealed bottles. Instruction to keep out of reach of children.

Placebo Group:

Placebo group will be administered as two size 00 capsules (that are similar in appearance to the treatment capsules) to be taken 4 times per day. A 15-day supply of 120 capsules in manufacturer sealed bottles. Instruction to keep out of reach of children.

Both Groups:

Both groups will take a single 100,000 IU dose of Vitamin D3 on day 1 of the study, supplied as two 50,000 IU capsules contained in factor sealed blister packs. The use of D3 will be open label for both groups.

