6.2.2 FORMULATION, APPEARANCE, PACKAGING, AND LABELING

How Supplied: Participants will receive a manufacturer sealed bottle containing 120 capsules each (15day supply) of the study agent capsules. Each size 00 capsule will contain either placebo (brown rice flour) or 500mg resveratrol (Vita-Age, Vancouver, BC, Canada).

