6.2.4 PREPARATION

Unmodified commercially available RV capsules and manufacturer prepared placebo capsules contained in manufacturer sealed bottles will be re-labelled with the study instructions. The bottles that have been prepared with study instruction will be turned over to an independent statistical consulting service (professors from Capital University department of Mathematics, Computer Science, and Physics) who will prepare the randomization table. Steps will be put in place to temporarily differentiate placebo vs RV bottles. Tamper-resistant serialized (sequentially numbered) stickers will be assigned to placebo or RV and affixed to the appropriate bottles. Bottles will be returned to the research team differentiated only by their unique serial number. The randomization table will be kept by OSU's consulting service and forwarded to the DSMB. The research team will only get access to the randomization list only after the completion of the study.

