12.1.3 Certificate of Analysis for Prepared Capsules

Edmont	art Inc. 1 Street NW [name] [name] F [contact]		Analytical Services and Consultation
		REPORT #	90171-2
То	Vita-Age Nutrition	Date	6/24/2020
	[name] T [contact]	Received	2020/06/16

VITA-AGE RESVERATROL; Lot# 20680 (9	0171-2)
-------------------------------------	---------

Test	Specification	Test Result	Method	Analyst	Date	Loc.
Arsenic	N/A	<0.03 ppm	ICP-MS	Hſ	2020/06/23	AB
Cadmium	N/A	<0.02 ppm	ICP-MS	ΗL	2020/06/23	AB
Lead	N/A	2.02 ppm	ICP-MS	ΗL	2020/06/23	AB
Mercury	N/A	<0.02 ppm	ICP-MS	JH	2020/06/23	AB
1. Total Plate Count	N/A	<10 CFU/g	USP <2021/2022>	OM	2020/06/22	AB
2. Yeast & Mold	N/A	<10 CFU/g (Yeast); 600 CFU/g (Mold)	USP <2021/2022>	OM	2020/06/22	AB
3. S. aureus	N/A	Negative	USP <2021/2022>	OM	2020/06/22	AB
4. E. coli	N/A	Negative	USP <2021/2022>	OM	2020/06/22	AB
5. Salmonella	N/A	Negative	USP <2021/2022>	OM	2020/06/22	AB
Resveratrol	500 mg/capsule	460 mg/ 514.17 mg	HPLC-UV	SMC	2020/06/23	AB
		*Based on a unit w	eight of 514.17 mg			

Labs-Mart Testing Locations:

AB - [name]

1. [name] O Prepared by 2020/06/24 Approved by Date [name], Account Manager [name], QC Specialist Raw data are archived by Labo-Mart Inc. Results shown relate only to samples submitted and tested. Labo-Mart Inc. assumes no liability for the use of the results by any party. Testing may be completed at other Labo-Mart Incoations. Statement of conformity only applies to tests currently presented on our scope of accreditation. All required parts of the standard [17025] applicable to a test laboratory are met. Accreditation is location and parameter specific. The tests listed in this report may not be included in the current scope of accreditation. The sample[s] were provided by the customer as listed on this report and therefore results reported apply to the samples as received. Page 1 of 1

This analytical test report shall not be reproduced, except in full, without written permission from Labs-Mart Inc.

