12.2.2 CERTIFICATE OF ANALYSIS FOR PREPARED CAPSULES

RAFA RIVER NATURALS CANADA INC.

[name] [contact] [contact] Email: [contact]

CERTIFICATE OF ANALYSIS

Report Date: Product Name: Lot No: Customer:	June 10, 2020 Placebo Vegetarian Capsu 20677 Canton Global Trading	les	
Description	A clear, #00 vegetarian ca Filled with fine, dense pov		
Colour	Capsule: body-natural cap- natural Powder: Beige		
Odour	Characteristic		
Ingredients	Each capsule contains:		
	Brown Rice Flour		850 mg
	Magnesium Stearate		5 mg
Tests	Test Method	Limits	Results
Filling Weight Variation	USP <905>	855 mg ± 5%	Conform
Gross Weight Variation		980 mg ± 5%	Conform
Disintegration	USP <701>	< 45 min.	Conform
Heavy Metal Testing	<maximum 5.<="" daily="" dose:="" th="">		</maximum>		
Arsenic	ICP/MS	< 0.14 µg/kg b.w/day	< 0.0109 µg/kg
Cadmium	ICP/MS	< 0.09 µg/kg b.w/day	< 0.0008 µg/kg
Lead	ICP/MS	< 0.14 µg/kg b.w/day	< 0.0008 µg/kg
Mercury	ICP/MS	< 0.29 µg/kg b.w/day	< 0.0008 µg/kg
Microbiological Testing	USP <2021>,<2022>	100.000 (/	
Standard Plate Count		<100,000 cfu/g	Conform
Escherichia coli		Negative	Negative
Salmonella		Negative	Negative
Staphylococcus aureus		Negative	Negative
Yeast and Mold		<10,000 cfu/g	Conform
Packaging	120 capsules / 225cc bottl	e	
Expiry Date	01/2022 (Not Labeled)		
Storage	Sealed, Store in a cool, dry Keep out of reach of child		
	Reep out of reach of child	ren	
	too the	6/10	12020

[figure not shown]
Quality Assurance/Quality Control

6/10/2020 Date

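### The placebo capsule weighs about 1.5 times the resveratrol capsule, and nothing in the plan matches or masks weight, so the blind is unprotected for staff who hold the coded bottles

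*Combined protocol and SAP*

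**What the plan says.** The trial is titled double-blind. Section 4.1 describes "identical-looking packets with identical-appearing study agents" and says study personnel are blinded to what the packets contain. Section 6.1.1 says the placebo is "to be prepared to be visually indistinct from the treatment capsules" and describes the active product as "Relabeled bottled containing size 00 capsules of resveratrol from commercially available bottles". Section 6.1.2 uses weaker wording for the placebo capsules: "that are similar in appearance to the treatment capsules". Section 6.2.2 adds: "Participants will receive a manufacturer sealed bottle containing 120 capsules each".

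Under section 6.2.4, bottles are re-labelled and handed to an independent third party, which attaches sequentially numbered stickers. Then: "Bottles will be returned to the research team differentiated only by their unique serial number". All of these standards concern appearance or labelling. None concerns weight.

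The appendix holds certificates for the lots that section 6.1.1 names as the prepared capsules:
- **Placebo, lot 20677 (12.2.2).** Fill 855 mg and gross 980 mg, each ±5% and reported as conforming. The powder is beige, and the shell is described as "A clear, #00 vegetarian ca" (the text breaks off there).
- **Resveratrol, lot 20680 (12.1.3, prepared capsules).** The assay result is "460 mg/ 514.17 mg", where the second figure is the unit weight. The certificate does not say whether this is fill or gross.

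The planned check on the blind (section 4.1) asks patients to guess their arm at about day 21. Staff are not asked.

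**The concern.** If the two products differ clearly in weight, a coded bottle carries a second identifier that needs no opening and no access to the randomization list. The protocol itself contains the certificates that show which product is heavier, and section 6.2.1 makes the investigator or designee responsible for receiving each shipment.

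Two things would be exposed:
- **Upcoming allocations.** Section 4.1 has designated personnel arrange pickup or delivery of the packet next in sequence. Anyone holding the numbered stock could learn the next arm beforehand.
- **Staff judgements after allocation.** The main ones are adverse event relatedness (8.3.3.2), which under 9.4.6 can suspend enrollment when a Grade 3 or higher event is judged probably or definitely related; the exit interview; investigator withdrawal (7.2); and, under the section 3 endpoint definition, whether an admission was for treatment of COVID-19.

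Each patient sees one product, so the day-21 patient question would not detect unblinding among staff.

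**Working it through.** **Inputs.** Placebo: 850 mg flour, 5 mg magnesium stearate, 980 mg gross, ±5% (12.2.2). Resveratrol: 460 mg assayed in a 514.17 mg unit (12.1.3); raw material at 98% (12.1.2A and 12.1.2B). Count: 120 capsules per bottle (6.1.2, 6.2.2). Not given: the resveratrol shell weight and the empty-bottle weight.

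1. **Reproduce the certificate.** Placebo fill = 850 + 5 = 855 mg, as stated. Implied placebo shell = 980 − 855 = 125 mg.

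2. **Is 514.17 mg fill or gross?** If gross, at most 514.17 − 460 = 54.17 mg is left for the shell, against 125 mg for the placebo shell of the same size 00. With a 125 mg shell the fill would be 514.17 − 125 = 389.17 mg, less than the 460 mg assayed. As a second check, 0.98 × 514.17 = 503.9 mg, close to the 500 mg label. Both point to fill weight.

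3. **Gross weight per capsule.** Resveratrol = 514.17 + 125 = 639.17 mg (same shell assumed). Ratio = 980 / 639.17 = 1.53. Over the placebo limits: 0.95 × 980 / 639.17 = 1.46 and 1.05 × 980 / 639.17 = 1.61. On fill alone: 855 / 514.17 = 1.66.

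4. **Sensitivity to the shell assumption.** For the gross weights to be equal, the resveratrol shell would have to weigh 980 − 514.17 = 465.83 mg, about 3.7 times the placebo shell.

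5. **Contents per bottle.** Placebo 120 × 0.980 = 117.6 g; resveratrol 120 × 0.63917 = 76.7 g; difference 40.9 g. Placebo at its lower limit is 0.95 × 117.6 = 111.7 g. Resveratrol 5% heavy (assumed, since no limit is given) is 1.05 × 76.7 = 80.5 g. The gap is still about 31 g.

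6. **Whole bottle.** The empty-bottle weight is assumed to be 20 to 60 g in both arms. At 20 g: 137.6 / 96.7 = 1.42. At 60 g: 177.6 / 136.7 = 1.30.

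| Quantity | Placebo | Resveratrol | Ratio |
|---|---|---|---|
| Fill per capsule, mg | 855 | 514.17 | 1.66 |
| Gross per capsule, mg | 980 | 639 | 1.53 |
| Contents per 120, g | 117.6 | 76.7 | 1.53 |
| Whole bottle, 20 g empty (assumed), g | 137.6 | 96.7 | 1.42 |
| Whole bottle, 60 g empty (assumed), g | 177.6 | 136.7 | 1.30 |

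**The case against.** Sections 4.1, 6.1.1 and 6.1.2 promise a match in appearance, and a weight difference does not contradict that. This stands: the conflict is with section 6.2.4 alone.

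Three stronger readings are tempting, and the documents do not support them.

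- **A ratio near 1.9.** Dividing 980 by 514.17 gives 1.91, but that treats 514.17 mg as gross and leaves no more than 54 mg for the shell. The ratio felt in the hand is also lower than the ratio of contents, because the bottle adds the same weight to both arms.
- **A visible colour difference.** The placebo powder is beige; the resveratrol raw material is white, or off-white in the stability report. But the active capsule's shell and both bottles' opacity are not in the readable text, and the bottles are sealed. A difference is possible, not shown.
- **The blind cannot hold, or concealment is lost.** Section 4.1 puts eligibility checks and consent before the packet is arranged, so looking at a bottle at that stage is too late to select the patient. Selection would need someone to inspect upcoming stock in advance. The documents do not say that the same people screen, handle bottles and assess outcomes, or that anyone will compare weights.

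The plan also limits some routes to bias. Section 9.4.2 establishes hospitalization from medical records and adjusts for age, sex, race, ethnicity and risk group. Much adverse event data comes from patient questionnaires, and the section 5.5 triggers for a dose-reduction offer come from the patient. What remains is mainly relatedness grading, exit interviews, investigator withdrawal and attribution of admissions. These points reduce the likely bias but do not remove the weight cue, and no step in the plan addresses it.

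**Conclusion.** The concern holds as a risk to the blind among staff. By the protocol's own certificates the placebo capsule is about 1.5 times as heavy, with about 41 g more contents per bottle. Returned bottles can therefore be told apart by more than a serial number, and the section 6.2.4 statement is not correct. Staff who hold both kinds of bottle could sort them by weight and, from the certificates, name the arm. Neither the staff blind nor the concealment of upcoming allocations is protected, and the patient-only check would not reveal a breach.

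The size rests on two assumptions: that 514.17 mg is fill weight, which the 460 mg assay supports, and that the active shell weighs about the same as the placebo shell. The whole-bottle ratio of about 1.3 to 1.4 also rests on an assumed 20 to 60 g bottle. The direction does not depend on the exact shell weight. The documents give no basis for estimating any resulting bias in the treatment effect.

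**What to change.** - **Section 6.2.4, masking.** Have the third party that already assigns the serial stickers seal each coded bottle in an opaque carton, ballasted to one common weight and numbered on the outside. Study personnel then store and deliver only cartons.
- **Section 6.2.4, wording.** Correct the statement that the serial number is the only difference between returned bottles.
- **Documentation.** Record the resveratrol capsule's gross weight and shell colour, and the opacity of the bottles. Keep the claims of identical or indistinguishable appearance in 4.1 and 6.1.1 only if that record confirms them.
- **Section 4.1, blinding check.** Ask the staff who do exit interviews, relatedness grading and chart review for a treatment guess, alongside the patient question.

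This needs about 200 cartons with ballast, a few hours of third-party packing, a short delay and a brief protocol edit. No dose, eligibility rule or analysis changes, so it is a cheap improvement. It has to be in place before bottles are dispensed, because concealment cannot be restored afterwards.

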6.1.2 DOSING AND ADMINISTRATION

Treatment Group: Two capsules containing resveratrol 500mg each will be taken 4 times per day. A 15day supply of 120 capsules in manufacturer sealed bottles. Instruction to keep out of reach of children.

Placebo Group:

Placebo group will be administered as two size 00 capsules (that are similar in appearance to the treatment capsules) to be taken 4 times per day. A 15-day supply of 120 capsules in manufacturer sealed bottles. Instruction to keep out of reach of children.

Both Groups:

Both groups will take a single 100,000 IU dose of Vitamin D3 on day 1 of the study, supplied as two 50,000 IU capsules contained in factor sealed blister packs. The use of D3 will be open label for both groups.

6.2 PREPARATION/HANDLING/STORAGE/ACCOUNTABILITY

6.2.1 ACQUISITION AND ACCOUNTABILITY

The investigator (or designated study personnel) is responsible for ensuring adequate accountability of study drug. This includes acknowledgement of receipt of each shipment of study drug (date, quantity, and condition), and subject dispensing records. Study dispensing records will document the dispensing of the study drug to individual subjects including the date dispensed, subject ID number, and initial of the person dispensing the study drug. Due to concerns of coronavirus contamination, unused study supplies will not be accepted for return and will be disposed of by the participant.

6.2.2 FORMULATION, APPEARANCE, PACKAGING, AND LABELING

How Supplied: Participants will receive a manufacturer sealed bottle containing 120 capsules each (15day supply) of the study agent capsules. Each size 00 capsule will contain either placebo (brown rice flour) or 500mg resveratrol (Vita-Age, Vancouver, BC, Canada).

6.2.3 PRODUCT STORAGE AND STABILITY

Storage at room temperature. Keep out of exposure to sunlight. Stability \geq 2 years.

6.2.4 PREPARATION

Unmodified commercially available RV capsules and manufacturer prepared placebo capsules contained in manufacturer sealed bottles will be re-labelled with the study instructions. The bottles that have been prepared with study instruction will be turned over to an independent statistical consulting service (professors from Capital University department of Mathematics, Computer Science, and Physics) who will prepare the randomization table. Steps will be put in place to temporarily differentiate placebo vs RV bottles. Tamper-resistant serialized (sequentially numbered) stickers will be assigned to placebo or RV and affixed to the appropriate bottles. Bottles will be returned to the research team differentiated only by their unique serial number. The randomization table will be kept by OSU's consulting service and forwarded to the DSMB. The research team will only get access to the randomization list only after the completion of the study.

6.3 MEASURES TO MINIMIZE BIAS: RANDOMIZATION AND BLINDING

After receipt of the intervention supplement and placebo, the third-party group will manage the randomization table. Research staff will be blinded to the randomization process.

6.4 STUDY INTERVENTION COMPLIANCE

Participants will document their compliance daily.

Noting that many patients will have a short duration of symptoms (in order to avoid unnecessary side effects), patients will be allowed to discontinue treatment after a minimum of 7 days if they have been symptom free for 3 days. Completion of a minimum of 7 days of treatment whose symptoms have resolved will be consider compliant with treatment.

In case of a single missed dosage, patient will be asked to divide the 2 missed capsules amongst their next 2 dosages. Patient is not to take more than 3 capsules at a time, and no more than 9 capsules in a day.

At the end of the study, participants will report the number of remaining capsules in their bottles at the end of 15 days.

6.5 CONCOMITANT THERAPY

For this protocol, a prescription medication is defined as a medication that can be prescribed only by a properly authorized/licensed clinician. Medications to be reported in the Case Report Form (CRF) are concomitant prescription medications, over-the-counter medications, and supplements.

Patients will be asked to discontinue any over-the-counter supplements/vitamins not prescribed by their physicians. Participants taking vitamin D prescribed by their physician will be asked to discontinue vitamin D for 1 month.

Patients on "statin" cholesterol lowering medication (e.g. simvastatin, lovastatin, etc.) and PDE-5 inhibitors (Viagra, Cialis, etc.) who would like to enroll in this study will be asked to discontinue these medications while on the study medication due to concerns for drug interactions. (Detampel, Beck, Krähenbühl, & Huwyler, 2012).

Patients on NSAIDs will be cautioned about increase risk of GI side effects and to avoid maximum dose NSAIDS. Patients on chronic high dose NSAIDS will be excluded from the study.

Noting that resveratrol is associated with increased insulin sensitivity, diabetics will be cautioned that the supplement could increase their risk of hypoglycemia and that they should monitor their blood glucose closely. (Poulsen, et al., 2013)

See also the exclusion criteria (section 5.2) for list of contraindicated medications.

Non-Trial Investigational Agents: During their participation in the study, subjects will be instructed against participating in other interventional clinical trials, or otherwise avoid taking non-trial investigational agents, unless they are hospitalized and/or their physician judges that participation in another clinical trial is necessary for obtaining the best health outcome after infection with SARS-CoV-2. If patient is prescribed hydroxychloroquine or chloroquine, they will be instructed to discontinue RV.

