2.3.2 KNOWN POTENTIAL RISKS

There are some concerns of adverse effects based primarily on in vitro studies and animal models (Shaito, et al., 2020). While human clinical trials have shown RV to generally be safe and well tolerated at single oral doses of up to 5g, dose related gastrointestinal upset has been reported (Ramírez-Garza, et al., 2018). High doses are associated with inhibition of cytochrome P450 (specifically CYP3A4, CYP2D6, & CYP2C9), which could result in some drug interactions, most concerning for drugs with a narrow therapeutic window. Drug interactions with nicardipine, warfarin, HIV protease inhibitors, anti-arrhythmics, calcium cancel agonists, antihistamines, and immunosuppressants have been reported in animal models (Shaito, et al., 2020). Hydroxychloroquine and chloroquine, drugs that are being investigated for use in COVID-19, are notably metabolized by CYP2C8 and CYP3A4. RV has been reported to enhance the replication of Hepatitis C virus in vitro (Nakamura, et al., 2010).

Noting that RV is associated with upregulation of ACE2 and ACE2 is the binding site for SARS-CoV2, increased ACE2 may facilitate viral entry into the cell (Yan, Xiao, & Lin, 2020).

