5.2 EXCLUSION CRITERIA

- Diagnosed or suspected cognitive impairment that would prevent the patient from cooperating with study procedures, as judged by the screening clinician.
- Asymptomatic patients (e.g. patients who were screened without symptoms but tested positive).
- Known history of cirrhosis, hepatic impairment, or Hepatitis C
- Known of history of renal impairment as measured by an eGFR of < 60 mL/min.
- Patients receiving chemotherapy or who are on chronic immunosuppressants.
- Allergy to grapes or rice.
- Co-morbidities with a high likelihood of hospitalization within 30 days (e.g., current cancer treatment, severe COPD or CHF)
- Currently pregnant

- Hospitalization
- Co-administration of "statins" and PDE-5 inhibitors must be withheld while on study treatment (see section 6.5).
- Due to concerns of patients taking immunosuppressants and drug interactions in medications with a narrow therapeutic index the use of the the following medications will be exclusionary (Blix, Viktil, Moger, & Reikvam, 2010) (Shaito, et al., 2020).

Immunosuppressants			
Generic Name Common Examples			

"Blood Thinners" / NOACs		
warfarin Coumadin		
rivaroxaban	Xarelto	
apixaban	Eliquis	
dabigatran	Pradaxa	

HIV Protease Inhibitors		
atazanavir	Reyataz	
darunavir	Prezista	
fosamprenavir	Lexiva	
indinavir	Crixivan	
lopinavir/ritonavir	Kaletra	
nelfinavir	Viracept	
ritonavir	Norvir	
saquinavir	Invirase	
tipranavir	Aptivus	
atazanavir/cobicistat	Evotaz	
darunavir/cobicistat	Prezcobix	

Immunosuppresants			
Janus Kinase Inhibitors			
tofacitinib	Xeljanz		
Calcineur	in Inhibitors		
cyclosporine	Neoral, Sandimmune, SangCya		
tacrolimus	Astagraf XL, Envarsus XR, Prograf		
mTOR inhibitors			
sirolimus Rapamune			
everolimus	Afinitor, Zortress		
IMDH inhibitors			
azathioprine Azasan, Imuran			
leflunomide Arava			
mycophenolate CellCept, Myfortic			
Bio	Biologics		

abatacept	Orencia	
adalimumab	Humira	
anakinra	Kineret	
certolizumab	Cimzia	
etanercept	Enbrel	
golimumab	Simponi	
infliximab	Remicade	
ixekizumab	Taltz	
natalizumab	Tysabri	
rituximab	Rituxan	
secukinumab	Cosentyx	
tocilizumab	Actemra	
ustekinumab	Stelara	
vedolizumab	Entyvio	
Monoclonal Antibodies		
basiliximab	Simulect	
daclizumab	Zinbryta	
other		
hydroxychloroquine	Plaquenil	
chloroquine	Aralen	

Seizure medications	
carbamazepine	Tegretol
phenobarbital	Luminol
phenytoin	Dilantin
valproate	Depakote

Cardiac medications	
amiodarone	Cardarone, Pacerone
digoxin	Lanoxin
flecainide	Tambocor
sotalol	Betapace

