7 STUDY INTERVENTION DISCONTINUATION AND PARTICIPANT DISCONTINUATION/WITHDRAWAL

7.1 DISCONTINUATION OF STUDY INTERVENTION

Discontinuation from study intervention does not mean discontinuation from the study, and remaining study procedures should be completed as indicated by the study protocol. If a clinically significant finding is identified (including, but not limited to changes from baseline) after enrollment, the investigator or qualified designee will determine if any change in participant management is needed. Any new clinically relevant finding will be reported as an adverse event (AE).

The study agent will be discontinued if the patient is admitted to the hospital.

The data to be collected at the time of study intervention discontinuation will include the following:

• Interview that participant regard their concern for discontinuation and assess for side effects/safety concerns.

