8.3.3.3 Expectedness

Research physicians will be responsible for determining whether an adverse event (AE) is expected or unexpected. An AE will be considered unexpected if the nature, severity, or frequency of the event is not consistent with the risk information previously described for the study intervention

Expected RV AE		
Diarrhea	Nausea	Gas/Bloating
Expected COVID AE		
Fever	Fatigue	Dry Cough
Loss of appetite	Body Aches	Shortness of breath
Mucus/phlegm	Sore Throat	Headache
Chills	Loss of smell/taste	Stuffy nose
Nausea or Vomiting	Diarrhea	Stroke
Conjunctivitis	Lower extremity numbness,	"COVID Toes"
	swelling, pain	
Arrhythmias	Heart Attacks	Cardiomyopathy
Pulmonary Embolism	Death	

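### Section 6.5 instructs stopping the study agent for newly prescribed hydroxychloroquine or chloroquine only; for other drugs in the 5.2 tables started as an outpatient, stopping rests on detection and investigator discretion (minor)

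*Combined protocol and SAP*

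**What the plan says.** The entry rule in 5.2 is firm. Because of concern about immunosuppression and about interactions with narrow-therapeutic-index drugs, "the use of the the following medications will be exclusionary", and tables of named drugs follow. Statins and PDE-5 inhibitors appear in 5.2 as a separate bullet with a different rule: the co-medication is withheld and the study agent continues.

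Section 6.5 carries the list into the treatment period by cross-reference: "See also the exclusion criteria (section 5.2) for list of contraindicated medications". It states no action for a listed drug that is started after randomization. The next paragraph, on non-trial investigational agents, ends with the only drug-specific stop: "If patient is prescribed hydroxychloroquine or chloroquine, they will be instructed to discontinue RV".

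Section 7.1 adds one mandatory stop, "The study agent will be discontinued if the patient is admitted to the hospital", and one general provision: after a clinically significant finding, "the investigator or qualified designee will determine if any change in participant management is needed". Section 7.2 lists a newly developed exclusion criterion that precludes further participation among the reasons for which an investigator may discontinue or withdraw someone.

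**The concern.** The stop instruction is narrower than the protocol's own interaction rationale. Section 2.3.2 names other drugs in the same paragraph as the chloroquine concern: "Drug interactions with nicardipine, warfarin, HIV protease inhibitors, anti-arrhythmics", among others. Warfarin and several anti-arrhythmics are in the 5.2 tables, yet a participant prescribed one of them in week 1 is given no stop instruction in the protocol.

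Such a start is foreseeable in people aged 45 or over with COVID-19. Section 8.3.3.3 lists "Pulmonary Embolism" and arrhythmias as expected COVID events, and 8.2 tells participants to seek care for a resting heart rate of 90 or more. At stake is the safety of a few participants, who could go on taking a concealed agent together with a drug that would have kept them out of the trial at entry.

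**Working it through.** No figure in the plan is in dispute. The check is a count, a side-by-side reading and an illustration of size.

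**Count of the 5.2 medication tables.** Anticoagulants 4; HIV protease inhibitors 11; immunosuppressant table 26 (JAK 1, calcineurin 2, mTOR 2, IMDH 3, biologics 14, monoclonal antibodies 2, hydroxychloroquine and chloroquine 2); seizure drugs 4; cardiac drugs 4; lithium, theophylline and rifampin 3. Sum: 4 + 11 + 26 + 4 + 4 + 3 = 52. With an explicit stop in 6.5: 2. Without: 52 − 2 = 50. The likeliest outpatient starts in this population are the 4 anticoagulants and 4 cardiac drugs, 8 of the 50. That selection is clinical judgement; a seizure drug or theophylline could also be started.

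**What happens after each event.**

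| Event during the course | Action in the protocol | Force |
|---|---|---|
| Hospital admission (7.1) | Study agent stopped | Mandatory |
| Pregnancy (8.3.9) | Participant asked to stop the agent | Explicit instruction |
| New hydroxychloroquine or chloroquine (6.5) | Participant told to stop the agent | Explicit instruction |
| Other new drug from the 5.2 tables, outpatient | Investigator may act (7.1, 7.2) | Discretionary, once known |

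Pregnancy is a useful comparison. It is on the same permissive 7.2 list, but 8.3.9 adds a direct instruction. A newly started contraindicated drug has no such addition.

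**How staff would learn of it.** Section 4.1 says the daily survey covers new medications and healthcare visits, but ties no action to the answer. Section 10.1.7 requires survey review at least weekly, and the notice on the daily questionnaire (12.6.1) warns that staff may not look at an entry for several days. A missed survey leads to a phone call (1.2); a completed survey that reports a new drug does not. Section 4.1 withholds the identity of the agent and has participants tell an outside provider that the trial involves a dietary supplement, so a prescriber cannot readily check for an interaction. No trial laboratory tests are planned (4.1).

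**Illustrative overlap.** Full dose: 2 capsules × 4 times × 500 mg = 4 g per day in the active arm. If the report is seen the next day: 1 × 4 g = 4 g (8 capsules). If it is seen at a 7-day review: 7 × 4 g = 28 g (56 capsules). At the reduced dose in 5.5 (1 capsule 4 times daily, 2 g per day) the figures are 2 g and 14 g. These describe duration, not interaction risk, and 28 g is not an upper bound, because a drug that is never reported is not caught at day 7.

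**Illustrative frequency.** The documents give no rate. Assuming 0.5% to 2% start one of the 8 drugs as outpatients: 0.005 × 200 = 1 to 0.02 × 200 = 4 participants, or 0.5 to 2 of the 100 on resveratrol.

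**Effect on the primary analysis.** Section 9.3 defines the intention-to-treat population as everyone randomized, and 9.4.2 uses it. Section 7.1 states "Discontinuation from study intervention does not mean discontinuation from the study, and remaining study procedures should be completed as indicated", and 7.2 follows even withdrawn participants for at least 21 days where allowed. A participant who stops the agent therefore still contributes a day-21 outcome.

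**The case against.** The strongest reply is that the sentence on hydroxychloroquine and chloroquine was never meant as the general rule. It closes a paragraph on investigational agents and deals with two drugs then being studied for COVID-19. The general position is the preceding line, which calls the 5.2 drugs contraindicated, backed by 7.2. The permissive verb in 7.2 also governs withdrawn consent and pregnancy, so it is weak evidence of real latitude. A new anticoagulant or anti-arrhythmic usually comes with a new diagnosis, which 7.1 makes a reportable adverse event, and 8.3.6 sends identified serious events to the principal investigator within 24 hours.

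Much of this stands. A reader might infer that the plan lets participants continue on any other listed drug. The documents do not support that: the drugs are called contraindicated and the investigator can act. What remains is that every one of these routes starts with staff finding out, and none tells the participant to stop at the time of the prescription.

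Three further cautions are accepted. The interaction reports in 2.3.2 come from animal models, and 2.3.1 cites a human trial at 1500 mg twice daily with no symptom attributed to altered drug metabolism, so known human harm should not be inferred. The consent pages, the diary front page and the bottle instructions are not visible in the text reviewed and may carry such an instruction, so the point is limited to the protocol's wording. Finally, 6.5 speaks of discontinuing the agent, which on its face is a 7.1 discontinuation; saying so explicitly is a clarification, not the repair of a contradiction.

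**Conclusion.** The point holds as a minor safety gap in wording. The explicit stop on a new prescription covers 2 of the 52 drugs in the 5.2 tables. For the other 50, started outside hospital, stopping depends on detection and discretion, and the required review interval allows several days of overlap. The expected number affected is small: 1 to 4 of 200 on an assumed 0.5% to 2% start rate, which has no source in the documents. The choice of 8 likely drugs is judgement.

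A reader might also infer that early stopping would bias or weaken the primary comparison. The documents do not support that: the analysis is by intention to treat, follow-up continues, and the numbers are very small.

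**What to change.** In 6.5, replace the hydroxychloroquine and chloroquine sentence with wording such as: *A participant newly prescribed any drug in the 5.2 medication tables (including hydroxychloroquine or chloroquine) stops the study agent and contacts the study team. This is discontinuation of study intervention under 7.1; surveys and follow-up continue. The separate rule for statins and PDE-5 inhibitors (withhold the co-medication) is unchanged.*

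Two details matter. The text should refer to the medication tables and not to 5.2 as a whole, which would catch statins and PDE-5 inhibitors and reverse their rule. It should say study agent and not RV, because the agent is concealed. Put the same instruction, with the drug names, in the participant packet.

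Cost: one replaced passage in 6.5 and one packet item, with no added visits, tests or sample size. Downside: a few participants in either arm stop the capsules early, but they remain in the intention-to-treat analysis.
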